Blood samples for pharmacokinetics (losmapimod concentrations) endpoints will be collected at Day 1, Week 4, Week 16, and Week 36 at the following timepoints: immediately pre-dose and 4 hours (± 30 minutes) after administration of the study drug. Blood samples for target engagement will be collected at Day 1 and Week 16 or Week 36 at the following timepoints: immediately pre-dose and 4 hours (± 30 minutes) after administration of the study drug. Musculoskeletal MRIs will be performed at screening, Week 12, Week 24, and Week 48. Muscle biopsies will be taken at Day 1 and Week 16, or at Day 1 and Week 36 if the muscle biopsy could not be performed at Week 16 due to the COVID-19 pandemic.

Safety and tolerability will be evaluated based on the assessment of adverse events (AEs), AEs of special interest (AESIs), serious adverse events (SAEs), laboratory tests, electrocardiogram (ECGs), vital signs, and physical examinations.

A schematic of the study design of the placebo-controlled treatment period is presented in [Figure 3-1](#).

Figure 3-1: Schematic of Study Design

Abbreviations: BID, twice daily; MRI, magnetic resonance imaging; OLE, open-label extension

During the open-label extension, subjects will be asked to attend clinic visits approximately every 12 weeks, and MRI will take place every 24 weeks. Study drug (open-label losmapimod) will be administered BID and should be taken with food. Subjects will remain in the open-label extension until study drug approval or until the study is discontinued by the Sponsor. All subjects who complete or discontinue from treatment will be asked to complete a 7-day safety follow-up period.

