8.3. MSK MRI Muscle Fat Fraction, Lean Muscle Volume and Muscle Fat Infiltration

Measurement of the extent of skeletal muscle tissue replacement by fat in FSHD patients will be done through automatic skeletal muscle segmentation for the 3D muscle volumes and fat fraction analysis via robust algorithms using Dixon imaging. This will be assessed at Screening, Week 12, and Week 48.

A. Composite measures: Composite variables, incorporating pre-selected muscles, will be derived for longitudinal analysis of muscle fat fraction, lean muscle volume and muscle fat infiltration (MFF_{tot} , LMV_{tot} , and MFI_{tot} respectively), as described in [Appendix 15.6](#). The scores will be derived by scientists at the MRI Service Provider (AMRA Medical Inc.) in a blinded fashion, with no access to treatment assignment information.

For each treatment, descriptive statistics of MFF_{tot} , LMV_{tot} , and MFI_{tot} per visit as well as changes from baseline will be presented. A Mixed Effect Model for Repeated Measures (MMRM) model will be used to analyze the change from baseline in each composite MRI score, with repeat number category, treatment group, visit, and treatment-by-visit interactions as fixed effects and baseline value of the parameter as a covariate. Within-group LS mean changes from baseline, the associated SEs and 2-sided 95% CIs, treatment differences in LS mean changes from baseline at Weeks 12 and 48 and the associated 2-sided 95% CIs and 2-sided p-values will be derived from the MMRM model and will be provided in the summary table. An unstructured covariance matrix will be used to model the correlation among repeated measurements within each subject. If models using unstructured covariance do not converge, an AR(1) covariance structured will be used instead. **LMV_{tot} is the key endpoint for hypothesis testing.**

B. Individual Muscles: For each muscle location, a similar method will be used to analyze muscle fat fraction (%), lean muscle volume (L), and muscle fat infiltration (%) per visit as well as changes from baseline.

The LS mean change from baseline by visit of the MSK MRI muscle fat fraction, lean muscle volume, and muscle fat infiltration will be graphically presented.

The change from baseline in the composite parameters will also be summarized by subgroups identified in [Section 4.6](#) to evaluate consistency of treatment effects across the subgroups.

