8.4.2. Classic and FSHD TUG

The TUG test is used to assess a person's mobility and requires both static and dynamic balance. It measures the time that a person takes to rise from a chair, walk 3 meters, turn around, walk back to the chair, and sit down. The FSHD TUG test is the classic TUG but adds the component of getting up from a laying position on a bed-like table in the clinic at the start of the test and laying

back down on his or her back at the end of the test. The FSHD TUG will capture total completion time and completion times for each segment (supine to sit, stand-walk-sit, and sit to supine). Each test will be done twice per visit and will be assessed at Baseline, Week 4, Week 12, Week 24, Week 36, Week 48, and Safety Follow-up. The average of Trial 1 and Trial 2 assessments at each visit will be derived for both the classic TUG completion time and each of the FSHD TUG completion times (ie, supine to sit, stand-walk-sit, sit to supine, and total) and will be used for the analysis.

For each treatment, descriptive statistics of classic TUG average completion time and FSHD TUG average completion times in seconds per visit as well as the change from baseline will be provided in tables. **The average completion time of the FSHD TUG is a key study endpoint, for hypothesis testing.** Descriptive statistics of FSHD TUG average completion times will be presented for each segment (supine to sit, stand-walk-sit, sit to supine, and total). An MMRM model will be used to analyze the change from baseline in classic TUG average completion time with repeat number category, treatment group, visit, and treatment-by-visit interactions as fixed effects and baseline value of classic TUG average completion time as a covariate. Within-group LS mean changes from baseline, the associated SEs and 2-sided 95% CIs, treatment differences in LS mean changes from baseline at post-baseline visits and the associated 2-sided 95% CIs and 2-sided p-values will be derived from the MMRM model and will be provided in the summary table. An unstructured covariance matrix will be used to model the correlation among repeated measurements within each subject. If models using unstructured covariance do not converge, an AR(1) covariance structured will be used instead. Similar methods will be used to analyze the change from baseline in FSHD TUG average completion times.

Similar analysis will also be conducted for each of the individual components of the FSHD TUG.

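### The only fallback covariance for the two Week 48 key-endpoint MMRMs is AR(1), which has one variance for all visits; a safer fallback costs little, although it should rarely be needed

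*SAP*

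**What the plan says.** SAP 8.1 puts DUX4, LMV at Week 48 and FSHD TUG at Week 48 in a fixed sequence, each tested at the final alpha from Table 12-1.

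SAP 8.3 analyses LMV by MMRM "with repeat number category, treatment group, visit, and treatment-by-visit interactions as fixed effects and baseline value of the parameter as a covariate". On covariance it says "An unstructured covariance matrix will be used to model the correlation among repeated measurements within each subject", followed by "If models using unstructured covariance do not converge, an AR(1) covariance structured will be used instead". On timing it says "This will be assessed at Screening, Week 12, and Week 48", which leaves two post-baseline visits. SAP 3.1 differs: "Musculoskeletal MRIs will be performed at screening, Week 12, Week 24, and Week 48". SAP 3.2.2 lists Week 24 MRI only where applicable.

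SAP 8.4.2 sets out the same model and fallback for classic TUG, then extends them: "Similar methods will be used to analyze the change from baseline in FSHD TUG average completion times". TUG is "assessed at Baseline, Week 4, Week 12, Week 24, Week 36, Week 48, and Safety Follow-up", so there are five post-baseline visits up to Week 48.

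The SAP addendum adds Kenward-Roger degrees of freedom (5.1). It repeats the same model and AR(1) fallback for the summed FSHD TUG segments (5.5). No heterogeneous fallback, robust standard error or baseline-by-visit term is named anywhere. The protocol (Synopsis, Statistical Methods; Section 7.6.3) lists the same fixed effects and is silent on covariance.

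**The concern.** AR(1), as the term is normally used, has one variance and one correlation; SAS names the heterogeneous version separately. Under that structure the Week 48 standard error rests on a variance pooled over all visits. If residual variance is larger at Week 48 than early on, the standard error is too small for the one comparison that counts. Kenward-Roger corrects the degrees of freedom and small-sample bias under the assumed covariance; it does not repair a wrong covariance.

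AR(1) also treats visits as equally spaced. For FSHD TUG the gaps are 8, 12, 12 and 12 weeks, a mild departure. For LMV with two visits there is only one correlation, so spacing does not matter.

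Separately, baseline enters as one main effect, so its slope is the same at every visit. If the relation to baseline changes over time, this costs some precision at Week 48.

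What is at stake is the error rate of two tests that the SAP places under type I control, in the event that the fallback is used.

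**Working it through.** **Inputs from the documents:** the model, fallback and visits above; two-sided alpha of about 0.05; 76 subjects planned and 80 enrolled. **Assumed, because the documents are silent:** every SD ratio, correlation and missing-data rate for the Week 48 endpoints.

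**1. The plan's own figure.** The only power statement concerns DUX4: effect size 0.70, 34 per group, 80% power. A two-sample t-test gives power 0.812 with 34 per arm and 0.7997 with 33. Then 68/0.9 = 75.6, rounded up to 76. This reproduces and is not affected by the present point.

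**2. Size of the unstructured matrix.** With T visits it has T(T+1)/2 parameters: 3 for LMV (T = 2), 15 for FSHD TUG (T = 5), and 6 for LMV if a Week 24 MRI enters (T = 3).

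**3. LMV under AR(1), two visits.** Let R be the Week 48 residual SD divided by the Week 12 residual SD. The fitted variance is the average of the two, so

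model SE / true SE = sqrt((1 + R²)/2) / R, and actual alpha = 2[1 − Φ(1.96 × that ratio)].

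For R = 1.5: sqrt(3.25/2)/1.5 = 1.275/1.5 = 0.850; 1.96 × 0.850 = 1.666; alpha = 0.096.

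| R | SE ratio | Actual alpha |
|---|---|---|
| 0.75 | 1.18 | 0.021 |
| 1 | 1.00 | 0.050 |
| 1.25 | 0.906 | 0.076 |
| 1.5 | 0.850 | 0.096 |
| 2 | 0.791 | 0.121 |

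**4. FSHD TUG under AR(1), five visits.** This is the limiting AR(1) fit with complete data, SD changing linearly from Week 4 to Week 48, under three correlation patterns.

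| SD at Week 48 / Week 4 | SE ratio | Actual alpha |
|---|---|---|
| 0.75 | 1.18 | 0.021 |
| 1.25 | 0.90 | 0.078 |
| 1.5 | 0.84 | 0.100 to 0.101 |
| 2 | 0.76 to 0.77 | 0.130 to 0.134 |

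**5. Why residual variance could rise.** What matters is the variance left after baseline adjustment. Suppose raw SDs are equal and the correlation with baseline is 0.95 at Week 12 and 0.85 at Week 48. With visit-specific slopes the residual SD ratio is sqrt((1 − 0.85²)/(1 − 0.95²)) = sqrt(0.2775/0.0975) = 1.69. With the SAP's common slope it is 1.72, and alpha under AR(1) is 0.109. If the correlation is the same at both visits (0.9 and 0.9), the ratio is 1 and alpha is 0.05.

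**6. Simulation and likelihood of use.** REML fits, 38 per arm, no treatment effect, about 15% missing in the main runs, fixed degrees of freedom in place of Kenward-Roger:

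| Case (runs) | Unstructured: rejection | AR(1): rejection | AR(1): SE ratio |
|---|---|---|---|
| LMV, equal raw SDs (1500) | 0.057 | 0.104 | 0.824 |
| LMV, Week 48 raw SD 1.2 times (1000) | 0.043 | 0.128 | 0.796 |
| FSHD TUG, five visits (250) | 0.044 | 0.104 | 0.818 |
| LMV plus a Week 24 MRI, 18% observed (300) | 0.060 | 0.123 | 0.805 |

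The unstructured model converged in every two-visit LMV and five-visit TUG run, and in 98% with the sparse Week 24 MRI. Taking that worst case, and treating non-convergence as independent of the test result:

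- R = 1.5: 0.98 × 0.05 + 0.02 × 0.096 = 0.0509
- R = 2: 0.98 × 0.05 + 0.02 × 0.121 = 0.0514

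Convergence was judged with a general optimiser, not SAS, so the 98% is indicative only.

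**7. Common baseline slope, unstructured covariance.** The Week 48 SE with a common slope, relative to visit-specific slopes, was 1.000 to 1.034 in all scenarios but one. It was 1.09 when the correlation with baseline fell from 0.9 at Week 12 to 0.5 at Week 48. Dropping the restriction therefore lowers the SE by 0 to 3% usually, and by 1 − 1/1.09 = 8% in that extreme case.

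**The case against.** The strongest reply is that the fallback will hardly ever be used. Three parameters for LMV and 15 for TUG are easily estimated from about 80 subjects, and the overall error rate then stays near 0.051. This stands, and it settles how much weight the point can bear.

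Second, the direction is assumed. The protocol describes a slowly progressing disease and gives no Week 48 to early-visit SD ratio; with falling variance the AR(1) test is conservative. This also stands. Step 5 shows that fading correlation with baseline is enough to raise residual variance without fast progression, but that too is an assumption.

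Third, a reader might infer that type I control of the hierarchy is broken. The documents do not support that. Harm needs non-convergence and rising variance together, and LMV is tested only after DUX4 succeeds, FSHD TUG only after LMV. If DUX4 has no effect, the familywise error is held by the DUX4 ANCOVA, which this does not touch.

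Fourth, heterogeneous structures are no remedy for LMV. With two visits and positive correlation, heterogeneous Toeplitz, AR(1) and compound symmetry have the same three parameters as the unstructured matrix. This is correct, and the LMV fallback has to be of another kind. It would change only if a Week 24 MRI entered the model.

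Fifth, a reader might infer that the common slope makes the Week 48 comparison invalid. It does not: under unstructured covariance the Week 48 standard error remains valid, and only efficiency is at issue.

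**Conclusion.** A worthwhile, inexpensive improvement to the specification. The AR(1) fallback is a poor choice for a Week 48 test. Conditional on its use, SD ratios of 1.25 to 2 give a type I error of about 8% to 13%, and a ratio of 0.75 gives about 2%. In the expected case the unstructured model converges and the stated analysis is sound; even with 2% non-convergence the overall rate is about 0.051. The conclusion rests on reading AR(1) as the one-variance form and on SD ratios that the documents do not supply. The common baseline slope is valid and usually costs 0 to 3% in Week 48 standard error. DUX4 and the sample size are unaffected.

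**What to change.** 1. **FSHD TUG (SAP 8.4.2; addendum 5.5).** Replace AR(1) with an ordered list, using the first that converges: heterogeneous Toeplitz, heterogeneous AR(1), heterogeneous compound symmetry.
2. **LMV (SAP 8.3).** Name one fallback that is a real alternative with two visits: either a structured covariance with sandwich standard errors, or an ANCOVA of change at Week 48. The sandwich option needs its own degrees-of-freedom rule, since Kenward-Roger is built on the model-based covariance. The ANCOVA gives up the Week 12 information on subjects without a Week 48 scan. State also whether any Week 24 MRI enters the model, as SAP 3.1, 3.2.2 and 8.3 differ.
3. **Optional.** Add baseline-by-visit to both models, with matching wording in the protocol (Synopsis, Statistical Methods; Section 7.6.3) and addendum 5.5.

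Cost: items 1 and 2 are a few sentences in the SAP and addendum, and change nothing if the unstructured model converges. Item 3 adds 1 parameter for LMV and 4 for FSHD TUG, plus a small protocol wording change so that the two documents agree.

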8.4. Clinical Outcome Assessments

8.4.1. Reachable Work Space With and Without Weights

The reachable work space (RWS) is a 3-dimensional sensor-based system (using a single depth-ranging sensor) that can unobtrusively detect an individual's RWS and reflects an individual global upper extremity function, including shoulder and proximal arm. The evaluation will be performed with and without weights and on both the right and left arms at Baseline, Week 4, Week 12, Week 24, Week 36, Week 48 and Safety Follow-up.

The absolute total RWS surface envelope area (m^2) as well as areas for each of the quadrants will be calculated and provided by a vendor in a blinded fashion, with no access to treatment assignment information. The reachable workspace relative surface area (RSA) represents the portion of the unit hemisphere that is covered by an individual's hand movement.

For each treatment, descriptive statistics of RSA results per visit as well as the change from baseline will be presented by quadrant, for total upper quadrants (Q1+Q3) and total area (Q1+Q2+Q3+Q4) for the assessment with weights and without weights, and by dominant and non-dominant arm. An MMRM model will be used to analyze the change from baseline in total area with repeat number category, treatment group, visit, and treatment-by-visit interactions as fixed effects and baseline value of the total area as a covariate. A separate model will be run with and without weights and for the dominant and non-dominant hand. Within-group LS mean changes from baseline, the associated SEs and 2-sided 95% CIs, treatment differences in LS mean changes from baseline at post-baseline visits and the associated 2-sided 95% CIs and 2-sided p-values will be derived from the MMRM model and will be provided in the summary table. An unstructured covariance matrix will be used to model the correlation among repeated measurements within each subject. If models using unstructured covariance do not converge, an AR(1) covariance structured will be used instead. Similar methods will be used to analyze the change from baseline in RSA for each quadrant.

Summary tables will be generated, showing percentage of subjects with RWS decline of $\geq 5\%$, $\geq 2\%$ at each post-baseline timepoint.

See [Section 4.6, #6](#) and [#7](#), for sub-group analyses to be conducted on this endpoint.

The functional work space (FWS) will also be summarized using number and percentages of subjects belonging to the categories of normal or low speed. The detected time within each target will be presented in a listing.

8.4.2. Classic and FSHD TUG

The TUG test is used to assess a person's mobility and requires both static and dynamic balance. It measures the time that a person takes to rise from a chair, walk 3 meters, turn around, walk back to the chair, and sit down. The FSHD TUG test is the classic TUG but adds the component of getting up from a laying position on a bed-like table in the clinic at the start of the test and laying

back down on his or her back at the end of the test. The FSHD TUG will capture total completion time and completion times for each segment (supine to sit, stand-walk-sit, and sit to supine). Each test will be done twice per visit and will be assessed at Baseline, Week 4, Week 12, Week 24, Week 36, Week 48, and Safety Follow-up. The average of Trial 1 and Trial 2 assessments at each visit will be derived for both the classic TUG completion time and each of the FSHD TUG completion times (ie, supine to sit, stand-walk-sit, sit to supine, and total) and will be used for the analysis.

For each treatment, descriptive statistics of classic TUG average completion time and FSHD TUG average completion times in seconds per visit as well as the change from baseline will be provided in tables. **The average completion time of the FSHD TUG is a key study endpoint, for hypothesis testing.** Descriptive statistics of FSHD TUG average completion times will be presented for each segment (supine to sit, stand-walk-sit, sit to supine, and total). An MMRM model will be used to analyze the change from baseline in classic TUG average completion time with repeat number category, treatment group, visit, and treatment-by-visit interactions as fixed effects and baseline value of classic TUG average completion time as a covariate. Within-group LS mean changes from baseline, the associated SEs and 2-sided 95% CIs, treatment differences in LS mean changes from baseline at post-baseline visits and the associated 2-sided 95% CIs and 2-sided p-values will be derived from the MMRM model and will be provided in the summary table. An unstructured covariance matrix will be used to model the correlation among repeated measurements within each subject. If models using unstructured covariance do not converge, an AR(1) covariance structured will be used instead. Similar methods will be used to analyze the change from baseline in FSHD TUG average completion times.

Similar analysis will also be conducted for each of the individual components of the FSHD TUG.

The change from baseline in the classic and FSHD TUG average completion times will also be summarized by subgroups [#8](#) and [#9](#), respectively, identified in [Section 4.6](#) to evaluate consistency of treatment effects across the subgroups.

8.4.3. Manual Dynamometry

Qualitative isometric dynamometry (hand-held dynamometer) will be used to assess the skeletal muscle strength of study subjects in both the upper and lower limbs bilaterally. Shoulders, flexors and extensors in the elbow, knees, and ankles as well as the grip bilaterally will be measured at each applicable visit. Isometric dynamometry measures the static muscle strength without any movement. This will be assessed at Baseline, Week 4, Week 12, Week 24, Week 36, Week 48, and Safety Follow-up.

For each treatment, descriptive statistics of average and maximum weight in kilogram per visit as well as the change from baseline will be presented by overall and according to assessment (right shoulder abductors, left shoulder abductors, right elbow flexors, left elbow flexors, right elbow extensors, left elbow extensors, right knee extension, left knee extension, right knee flexion, left knee flexion, right ankle dorsiflexors, left ankle dorsiflexors, right hand grip, and left hand grip). An MMRM model will be used to analyze the change from baseline in average weight with repeat

number category, treatment group, visit, and treatment-by-visit interactions as fixed effects and baseline value of average weight as a covariate. Within-group LS mean changes from baseline, the associated SEs and 2-sided 95% CIs, treatment differences in LS mean changes from baseline at post-baseline visits and the associated 2-sided 95% CIs and 2-sided p-values will be derived from the MMRM model and will be provided in the summary table. An unstructured covariance matrix will be used to model the correlation among repeated measurements within each subject. If models using unstructured covariance do not converge, an AR(1) covariance structured will be used instead. Similar methods will be used to analyze the change from baseline in maximum weight.

Similar analysis will be done for total average manual dynamometry for: (a.) all muscles combined; (b.) upper extremity strength, in the shoulders and elbows combined; and (c.) lower extremity strength, which includes right knee extension, left knee extension, right knee flexion, left knee flexion, right ankle dorsiflexors, and left ankle dorsiflexors muscles combined.

8.4.4. MFM Domain 1

The MFM scale assesses the severity of the motor deficit. It provides a clinician's assessment of functionality impairment for standing and transfers. Domain 1 has 13 items in version 1 and 15 items in version 3 of the protocol with each item scored from 0 to 3. The MFM Domain 1 score corresponds to the sum of the item scores divided by the maximum score for this dimension and multiplied by 100 (ie, sum of scores/39*100 for 13 items questionnaire and sum of scores/45*100 for the 15 items questionnaire). This will be assessed at Baseline, Week 12, Week 24, Week 36, and Week 48.

For each treatment, descriptive statistics of the MFM Domain 1 scores (individual item scores and Domain 1 score) per visit as well as the change from baseline will be presented. An MMRM model will be used to analyze the change from baseline in MFM Domain 1 score with repeat number category, treatment group, visit, and treatment-by-visit interactions as fixed effects and baseline score as a covariate. Within-group LS mean changes from baseline, the associated SEs and 2-sided 95% CIs, treatment differences in LS mean changes from baseline at post-baseline visits and the associated 2-sided 95% CIs and 2-sided p-values will be derived from the MMRM model and will be provided in the summary table. An unstructured covariance matrix will be used to model the correlation among repeated measurements within each subject. If models using unstructured covariance do not converge, an AR(1) covariance structured will be used instead.

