4.2. Handling of Missing Data

Missing data for primary efficacy endpoint will be handled as specified in the sensitivity analyses [Section 8.2.1](#).

All missing and partial dates for the prior/concomitant medications and adverse events will be handled as outlined in [Sections 7.1](#) and [9.1](#), respectively.

In categorical summaries, a missing category will be included if and only if any data for the given endpoint is missing.

Missing values for other individual data points will remain as missing, unless otherwise, stated.

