4.3. Baseline, Study Day, and Change from Baseline Definitions

Unless indicated otherwise, baseline will be defined as the last non-missing evaluation on or before the day of first dose of study drug. In the event that the last non-missing evaluation and the study drug administration happen on the same day, timing of the evaluation will be used to determine the pre- or post-dose. If timing is not available, the evaluation is considered pre- or post-dose based on the schedule of events for that assessment. For example, AEs and concomitant medication are considered post-baseline evaluations.

For muscle biopsies, any assessment taken on the first day of study drug exposure will be considered baseline, irrespective of timing to study drug.

Relative study days will be calculated as:

$(\text{assessment date} - \text{dose administration date}) + 1$

if the assessment date is on the same day or after the dosing date, otherwise:

$(\text{assessment date} - \text{dose administration date})$.

Study day will be presented on all listings where appropriate.

Change from baseline will be computed as (post-baseline assessment value - baseline assessment value).

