4.9.6. Open-label Losmapimod (Pre-COVID-19) Analysis Set

This analysis set will consist of subjects who were already transitioned into open-label losmapimod under version 3.0 of the protocol. This analysis set will be used for sensitivity analysis, to assess secondary/exploratory endpoints in this subset of subjects.

5. Subject Disposition

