Table	14.2.4.3.3	Change from Baseline in Total Average Dynamometry Result; All Muscles Combined, Upper Extremity, Lower Extremity	FAS	U	8.3.3	Efficacy		
Table	14.2.4.4.1	Shift in Motor Function Measure (MFM) Individual Component Score	FAS	U	8.3.4	Efficacy		

TLF	Table Number	Title	Analysis Set	Unique (U)/Repeat (R)	Section	Efficacy/Safety/Standard	Topline	IA
Table	14.2.4.4.1.1	Shift in Motor Function Measure (MFM) Individual Component Score	Open-label losmapimod (Pre-COVID-19) Analysis Set	R	8.3.4	Efficacy		
Table	14.2.4.4.2	Change from Baseline in Motor Function Measure (MFM) Domain 1	FAS	U	8.3.4	Efficacy		
Table	14.2.4.4.2.1	Change from Baseline in Motor Function Measure (MFM) Domain 1	Open-label losmapimod (Pre-COVID-19) Analysis Set	R	8.3.4	Efficacy		
Table	14.2.4.5	Change from Baseline in FSHD Health Index (FSHD-HI)	FAS	U	8.3.5	Efficacy		
Table	14.2.4.5.1	Change from Baseline in FSHD Health Index (FSHD-HI)	Open-label losmapimod (Pre-COVID-19) Analysis Set	R	8.3.5	Efficacy		
Table	14.2.4.6.1	Patients' Global Impression of Change (PGIC) Improved and Not Improved	FAS	U	8.3.6	Efficacy		
Table	14.2.4.6.1.1	Patients' Global Impression of Change (PGIC) Improved and Not Improved	Open-label losmapimod (Pre-COVID-19) Analysis Set	R	8.3.6	Efficacy		
Table	14.2.4.6.2	Patients' Global Impression of Change (PGIC)	FAS	U	8.3.6	Efficacy		
Table	14.2.4.6.2.1	Patients' Global Impression of Change (PGIC)	Open-label losmapimod (Pre-COVID-19) Analysis Set	R	8.3.6	Efficacy		
Table	14.3.1.1	Overall Summary of Treatment-Emergent Adverse Events	Safety Analysis Set	U	9.1	Safety	Y	
Table	14.3.1.1.1	Overall Summary of Treatment-Emergent Adverse Events	Open-label losmapimod (Pre-COVID-19) Analysis Set	R	9.1	Safety		
Table	14.3.1.2	Treatment-Emergent Adverse Events by System Organ Class and Preferred Term	Safety Analysis Set	U	9.1.1	Safety		

TLF	Table Number	Title	Analysis Set	Unique (U)/Repeat (R)	Section	Efficacy/Safety/Standard	Topline	IA
Table	14.3.1.2.1	Treatment-Emergent Adverse Events by System Organ Class and Preferred Term	Open-label losmapimod (Pre-COVID-19) Analysis Set	R	9.1.1	Safety		
Table	14.3.1.3	Treatment-Emergent Adverse Events by Relationship to Study Drug	Safety Analysis Set	U	9.1.2	Safety		
Table	14.3.1.3.1	Treatment-Emergent Adverse Events by Relationship to Study Drug	Open-label losmapimod (Pre-COVID-19) Analysis Set	R	9.1.2	Safety		
Table	14.3.1.4	Treatment-Emergent Adverse Events by Maximum Severity	Safety Analysis Set	U	9.1.3	Safety		

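### MFM Domain 1 is scored against a 13-item or a 15-item maximum by protocol version, so a change score that spans both forms is computable but not comparable

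*SAP*

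**What the plan says.** SAP 8.4.4 (MFM Domain 1) says that "Domain 1 has 13 items in version 1 and 15 items in version 3 of the protocol", with each item scored 0 to 3. The Domain 1 score is "sum of scores/39*100 for 13 items questionnaire and sum of scores/45*100 for the 15 items questionnaire". Assessments are at Baseline and Weeks 12, 24, 36 and 48. Change from baseline in this percentage goes into an MMRM with repeat category, treatment, visit, treatment-by-visit interaction and baseline score. There is no term for form.

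The general rule in SAP 4.3 is "Change from baseline will be computed as (post-baseline assessment value - baseline assessment value").

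The outputs in SAP 15.8 include "Change from Baseline in Motor Function Measure (MFM) Domain 1" for the FAS (Table 14.2.4.4.2) and again for the Open-label Losmapimod (Pre-COVID-19) set (Table 14.2.4.4.2.1). Of that set, SAP 4.9.6 says: "This analysis set will be used for sensitivity analysis, to assess secondary/exploratory endpoints in this subset of subjects".

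Protocol 6.4.4 gives no item count and leaves the instructions to a study reference manual. The SAP addendum does not mention MFM. No item count is given for protocol versions 2.0 or 4.0, and nothing says whether the 13 items are contained in the 15.

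**The concern.** Dividing by 39 or 45 puts both forms on a 0 to 100 scale, but it equalises the range and not the content. If baseline has 13 items and a later visit has 15, the two added items enter only the later score, so the difference can move when function has not.

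SAP 8.4.4 can be read in two ways: the form follows the protocol in force at each visit, or it follows the version under which the subject entered. On the first reading, some change scores mix forms. On the second, none does, but the MMRM still treats 13-item and 15-item scores as one outcome and one baseline covariate.

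The most exposed output is Table 14.2.4.4.2.1. It reports MFM change in the early rollover subjects, where within-group change is read directly and a form effect would not cancel between arms.

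**Working it through.** **1. The plan's own figures.** Maximum raw score is items times 3: 13 × 3 = 39 and 15 × 3 = 45. Both denominators in SAP 8.4.4 reproduce.

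**2. Could any subject have been measured on both forms?**

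- Week 24 is Day 168 (SAP Table 4-1) with a window of ±5 days (protocol Table 13-1), so the earliest Week 24 visit is Day 163, which is 162 days after Day 1.
- Twelve subjects had rolled over at Week 24 by 10 April 2020 (protocol 3.1.1). Their latest possible Day 1 is 10 April 2020 minus 162 days, or 31 October 2019.
- Version 3.0 is dated 27 November 2019. A subject with Day 1 on that date would have been 135 days past Day 1 on 10 April 2020, short of 162.
- All 12 therefore had Day 1 before version 3.0. The protocol-version memo says that sites in the USA, Canada, France and Spain went from version 1.0 directly to version 3.0; version 2.0 went to Germany only.
- These subjects rolled over under version 3.0. If the form followed the protocol in force, the non-German ones had 13 items at baseline and 15 at Week 24. Others enrolled before version 3.0 took effect at their site would be in the same position.
- Not given: the number of German rollovers, the number of such other subjects, and the form used at Weeks 36 and 48 under version 4.0.

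**3. What a change of form does to the score (illustration).** Assume that the 13 items are nested in the 15 and that function is unchanged. Let S be the sum of the 13 common items and e the sum of the two added items (0 to 6). Then

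shift = 100(S + e)/45 − 100S/39, which is zero only when e = 6S/39.

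| S | 13-item score | shift at e = 0 | shift at e = 6 |
|---|---|---|---|
| 39 | 100.0 | -13.3 | 0.0 |
| 30 | 76.9 | -10.3 | +3.1 |
| 20 | 51.3 | -6.8 | +6.5 |
| 0 | 0.0 | 0.0 | +13.3 |

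For S = 30 the neutral value is 6 × 30/39 = 4.62, which whole-number item scores cannot give. The nearest sums, 4 and 5, shift the score by -1.4 and +0.9. A subject at the 13-item ceiling can only stay level or fall.

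**4. After the proposed change.** With both visits scored on the 13 common items, the shift is 100S/39 − 100S/39 = 0 for every S.

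**The case against.** **A rule exists.** A reader might infer that the SAP leaves the calculation undefined. It does not: each visit is scored against its own form's maximum and SAP 4.3 subtracts, so two programmers would get the same number. This stands. The fault is that the number is not comparable across forms.

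**No change of form is shown.** A reader might also infer that subjects did switch. The documents do not say so. The summary of changes for version 3.0 lists specific edits to protocol 6.4.1, 6.4.7 and 6.4.8 but none to 6.4.4, and the version 2.0 and 4.0 summaries list no MFM change. The only evidence of two forms is the SAP sentence, and the dates show when baseline occurred, not which form was used. The reference manual or the table shells, neither of which is available, could fix the form per subject. This stands as a limit. It does not remove the gap, because the SAP defines the score and does not choose between the two readings.

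**The size is illustrative.** The documents contain no MFM scores. The value 30/39 and the values of e are chosen, and at other starting scores the range and even the sign differ. A mean shift for the rollover set or for the FAS treatment difference would also need the number who changed form and their scores, so none is claimed.

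**The item-level shift table.** One might think that "Shift in Motor Function Measure (MFM) Individual Component Score" also needs a new rule. SAP 4.2 already covers it: "Missing values for other individual data points will remain as missing, unless otherwise, stated". An item absent at baseline has no category to shift from.

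**Conclusion.** The point holds as a minor one. As written, SAP 8.4.4 and 4.3 give a change score that is not comparable for any subject measured on both forms, and the MMRM mixes the two forms without adjustment or a sensitivity analysis. Whether this affects anyone is unconfirmed. It would affect the non-German subjects among the 12 rollovers if the form followed the protocol in force at each visit.

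The per-subject illustration (-10.3 to +3.1 points at 30/39) rests on nesting, unchanged function and a chosen score. The effect on any table cannot be derived from the documents.

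A reader might infer a biased treatment comparison or a threat to the trial's conclusions. The documents do not support either. The form would follow calendar time and not randomised arm, so no systematic bias between arms is expected. MFM Domain 1 is exploratory (SAP 3.2.3), is not in the sequence in SAP 8.1, and falls under protocol 7.6.4, which gives exploratory comparisons no confirmatory value.

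**What to change.** In SAP 8.4.4:

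- State which form applies at each visit, including under versions 2.0 and 4.0, and whether the 13 items are contained in the 15.
- If they are, compute Domain 1 from the 13 common items (sum/39 × 100) at baseline and all post-baseline visits for any subject measured on both forms. Use this in the MMRM and the Domain 1 summaries, including Table 14.2.4.4.2.1.
- Add a sensitivity analysis scoring every subject on the common items. This also addresses the pooling of forms across subjects who stayed on one form.
- Report the number who changed form, by arm.
- If the items are not nested, score the items that the two forms share. Use same-form visit pairs only as a sensitivity analysis.
- If no subject changed form, say so; the rescoring for subjects measured on both forms is then not needed.

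The cost is SAP wording and a small scoring change. No new data are needed, because the SAP already plans "descriptive statistics of the MFM Domain 1 scores (individual item scores and Domain 1 score) per visit". The two added items go unused for subjects who changed form, and for everyone in the sensitivity analysis.

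Same-form pairs cost more. Unless version 4.0 went back to 13 items, which is not stated, affected rollover subjects would lose Weeks 24, 36 and 48 and keep at most Week 12, before open-label treatment. Table 14.2.4.4.2.1 would then lose their open-label data, which is why this option should not be the main analysis.
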